Conduct a 1:1 pilot randomized controlled trial of the SOVA Peer Ambassador Program compared to attention control: brief psychoeducational independent assignments (i.e. reading SOVA articles and responding to open-ended questions without content creation and without peer interaction) (N=40) and evaluate feasibility of implementation strategy. All participants will have access to read content on the SOVA sites, but only Ambassadors will be able to log-in and invited to create content to share with others. We will examine participant adherence to intervention feasibility and acceptability of intervention, attention control, and implementation strategy. We will also assess acceptability of randomization, feasibility of recruitment, quality of training, trainer fidelity. We will generate preliminary data on outcomes, refine proposed study measurements, and assess preliminary effectiveness on resilience.

Study Design & Methods

This intervention trial will use a randomized trial design where each of the 40 participants is randomly assigned to one of two arms. Adolescents will be randomized at a 1:1 ratio (using randomized block sizes). The arms are SOVA Peer Ambassador Program and attention control: brief psychoeducational independent assignments.

1) conduct a pilot RCT comparing SOVA Peer Ambassador Program to attention control to understand feasibility and acceptability of Ambassador Program and accompanying implementation strategy. Adolescents will be randomized at a 1:1 ratio (using randomized block sizes). The primary endpoint is feasibility of the intervention. Expected Outcomes: We anticipate to learn if the SOVA Peer Ambassador intervention is feasible in a work readiness program setting for low-income adolescents consisting of mostly racial minority youth. We also anticipate to understand feasibility and acceptability of the attention control, implementation strategy, refine proposed study measurements, measure cross-over between groups, and find if there is preliminary effectiveness.

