If randomized to the SOVA Ambassador arm, the research assistant will provide an onboarding tutorial of the SOVA website contribution expectations. First, users will be asked to provide a username and email they would like to use for the website. The research assistant (RA) will create a login for them for the site. Participants will be asked to not post identifying information on the site and if they do, the site moderator will remove it. By creating a username, they will receive weekly email notifications about new posts. Participants will be notified that the researchers will use the website to track log-in frequency, log-in duration frequency, and website use. Also, any online text will be downloaded and qualitatively analyzed as well - unless the text contains identifying information - in that situation, this content will be permanently deleted. The Ambassador phone call will include information about compensation, blogging expectations, and procedures. There will be disclaimer about safety tips, and reminding participants this website is not an alternative to therapy or other treatment. The RA will share expectations of participating in the SOVA intervention which is to contribute content to the SOVA website at least once a month either by (1) writing a blog article. They can choose what they would like to write about and they will work with a SOVA team member who will edit and provide thoughtful feedback. They will be encouraged to • share personal experiences • share stories • give advice to other members (2) sending information (de-identified photo or video or music) to post. If they choose this option they will be encouraged to submit their own photo, video, or music to the website or they will be encouraged to write a response to a photo, video, or music piece. (3) being interviewed by the RA and then the RA "ghostwriting" an article about the interview which they pre-approve prior to it being posted. • If they choose this option they will get a series of topics and questions to choose from. e.g. people often can disagree – family, friends, partners, co-workers, or random people, offline or online, can you talk about how disagreements in your or others' lives can affect your stress or mental health? If randomized to the Attention Control arm, the research assistant will provide an onboarding tutorial of the expected contributions. This will include going to redcap form where they will receive a link to a SOVA article to read and a question for them to answer about what they read that will be accessible only to the study team. They will be asked to do this a couple times a month and will be reminded about their participation. The articles will be about mental health found on the website sova.pitt.edu. The question asked of the participants in this study arm will be open ended. An example of this will be: The article talked about different types of therapy. What types of therapy do you have experience with? If you do not have experience with the types of therapy which type of therapy do you think is most interesting? Then describe why or why not. Both arm participants will fill out online surveys via REDCap at baseline 6 weeks and 12 weeks. These surveys will take about 30 minutes to complete.

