Data analysis: Our main goal is to understand feasibility of the pilot trial. Engagement with the SOVA Peer Ambassador intervention will be the main outcome and will be determined by the average number of articles written per participant at 12 weeks. We will use summary statistics (frequencies and percentages for categorical variables; means (standard deviations); and medians (ranges) for continuous measures) to describe measures. We will follow all recommendations from the pilot CONSORT statement. We will record number, percentage survey items missing and will summarize. We will capture proximal and main outcomes listed in Table 1 by study arm and assess change (from baseline to 6-week, and baseline to 12-week) using a linear mixed model for continuous outcomes. We will use a linear mixed model to estimate initial associations between treatment arm and resilience outcomes. The statistician conducting analyses will be blinded to randomized arm. Sample size: Feasibility of the intervention will be established if an average of 2.3 articles are written per individual over the 12 weeks. This is because anticipating a SD of 0.5, that would give us a confidence interval width of 0.59 with a sample of $N = 20$. If results are very skewed, we will log transform any outliers. We have designated this sample size due to budgetary and programmatic constraints. Expected Outcomes: We anticipate to learn if the SOVA Peer Ambassador intervention is feasible in a work readiness program setting for low-income adolescents consisting of mostly racial minority youth. We also anticipate to understand feasibility and acceptability of the attention control, implementation strategy, refine proposed

study measurements, measure cross-over between groups, and find if there is preliminary effectiveness.

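### The stated blinding of the statistician cannot hold for the Ambassador-only main outcome, and the plan does not say how it is kept for the between-arm analyses

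*Combined protocol and SAP*

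**What the plan says.** The Data analysis text under Statistical Considerations appears twice in nearly the same words. Both copies define the main outcome: "Engagement with the SOVA Peer Ambassador intervention will be the main outcome and will be determined by the average number of articles written per participant", taken at 12 weeks. Both then plan the comparative work: "We will capture proximal and main outcomes listed in Table 1 by study arm" and "We will use a linear mixed model to estimate initial associations between treatment arm and resilience outcomes". The next sentence in both is "The statistician conducting analyses will be blinded to randomized arm".

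The arms are described earlier. Under Study Objectives, everyone may read the SOVA sites, but "only Ambassadors will be able to log-in and invited to create content to share with others". The control activity is "reading SOVA articles and responding to open-ended questions without content creation and without peer interaction". Under Study Design & Methods, Ambassadors are told that "the researchers will use the website to track log-in frequency, log-in duration frequency, and website use", while control participants take part by "going to redcap form where they will receive a link to a SOVA article to read and a question for them to answer".

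The document describes no coded arm labels, separate data files, order of analysis, second analyst for the engagement data, or time at which the blind is broken.

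**The concern.** A statistician cannot be blind to arm when analysing a variable that only one arm can produce. As worded, the plan claims a property that its main analysis does not have, and a trial report repeating the sentence would be inaccurate on that point.

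There is a second, conditional issue. Analyst blinding is useful mainly for the between-arm comparison of resilience. That model is described in one sentence, with no covariates, covariance structure or rule for missing data, so the analyst still has choices to make. If engagement records reach the same person first and can be matched to the survey file, coded arm labels no longer hide the allocation. The plan contains nothing that prevents this, and nothing that says it will occur.

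**Working it through.** No sample size, power or error rate depends on this point. The check sets the statements side by side and then asks what would reveal the codes.

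**1. Is the main outcome confined to one arm?**
- Log-ins and invitations to create content go to Ambassadors only (Study Objectives).
- Controls read articles and answer questions in REDCap, without creating content (Study Objectives; Study Design & Methods).
- The precision statement uses SD 0.5 and N = 20, and the planned split is 20 intervention and 20 control (Statistical Considerations).

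The plan's figure for that statement is a confidence interval width of 0.59, with no confidence level given. The ordinary 95% width is 2 × t(0.975; 19) × SD/√n = 2 × 2.093 × 0.5/√20 = 0.468. Allowing 95% assurance for the sample SD gives 0.468 × √(χ²(0.95; 19)/19) = 0.468 × √(30.14/19) = 0.589, which rounds to 0.59. The document does not name that variant, and the present point does not rest on it. What matters is that N = 20 is one arm. So the main outcome is planned on Ambassadors alone.

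**2. Can the analyst of that outcome be blind?** No. Being in the analysis set is itself knowledge of the arm.

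**3. Can the resilience models be run blind?** Yes. They need the survey data and an arm label, and the label can be A or B. Nothing in the design prevents this.

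**4. What would reveal the codes?** Three things together: participant-level engagement data, a link from those data to the survey file, and sight of them before the models are final.
- If the engagement file lists only Ambassadors, presence in it identifies the arm, whatever the count.
- If controls are also listed, with zero articles, only non-zero counts identify anyone. As an illustration, assume Poisson counts; this assumption is not in the documents. The expected number of Ambassadors with at least one article is 20 × (1 − e^(−m)), and the chance that at least one has an article is 1 − e^(−20m).

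| Assumed mean m | Expected Ambassadors identified, of 20 | Chance of at least one |
|---|---|---|
| 2.3 (the plan's feasibility threshold) | 18.0 | above 0.9999 |
| 1 | 12.6 | above 0.9999 |
| 0.5 | 7.9 | above 0.9999 |

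Since only Ambassadors hold log-ins, one linked non-zero record shows which code is the Ambassador arm, and hence the allocation of the rest. The table says what follows if the three conditions are met. It says nothing about how likely they are.

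**The case against.** The strongest reply is that the blinding sentence directly follows the resilience mixed-model sentence, so it may be meant for that model only, where coded arms make blinding feasible. That is a reasonable guess at the intent. The words do not say so, however: they refer to the statistician conducting analyses, in a paragraph that opens with the main outcome. Even on the narrower reading, the plan does not say how the blind is kept.

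A reader might infer that opening the engagement data necessarily unblinds the resilience comparison, or that every participant is unblinded. The documents do not support this. They do not say who computes the article mean, and the study team could supply it as a single figure. They do not say that website records and survey data will be linked, or which analysis comes first. This part of the objection stands: the leak is a risk and not a certainty.

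A reader might also infer that the plan leaves outlier and skew handling of the survey outcomes to an unblinded analyst. The sentence on log-transforming outliers sits with the article-count precision text and is not tied to the survey outcomes. On missing survey items, the plan says only that they will be counted and summarised.

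The plan also expects to measure cross-over, so separation of the arms is not treated as guaranteed. This does not rescue the claim: articles are still an Ambassador activity by design, and measuring cross-over itself requires knowledge of the assigned arm.

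**Conclusion.** The concern holds in a limited form. The blinding statement cannot be true for the article-count analysis; this follows from the design alone and needs no assumption. For the resilience and other between-arm survey models, blinding is achievable but unprotected. It fails only if the same statistician sees linkable participant-level article or log-in data before those models are run, and the documents are silent on this. It would be wrong to say that the trial cannot be analysed blind at all, or that its comparative results will be unblinded.

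The consequence is modest. The main outcome is a one-arm descriptive mean set against a threshold of 2.3 articles, for which analyst blinding matters little. Resilience is a preliminary outcome in a pilot of 40, with no decision rule attached. What is at stake is accurate reporting of who was blinded to what, and protection of the planned comparison between arms. The change should be made because it corrects a stated property that the design does not have, at very little cost.

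**What to change.** In both copies of the Data analysis text:

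1. Limit the blinding statement to the between-arm analyses of survey outcomes.
2. State that those mixed models are run and locked with arms coded A/B, on a file that holds no article counts, log-in data, control-assignment answers or other arm-specific items such as acceptability of one arm's activity.
3. State that engagement data are released to the statistician only after that lock. Alternatively, have an existing team member summarise the article counts separately, so that the statistician does not receive them at participant level beforehand.
4. Describe the article-count analysis, and any other analysis that needs the assigned arm (such as cross-over), as unblinded.

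The cost is one extra data extract and a fixed order of analysis. No extra staff are needed; the engagement analysis may be slightly delayed if it waits for the lock.
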